6.4 Peri-operative Care

Refer to institutional protocols for peri-operative management of patients undergoing treatment for aortic dissection.

6.5 Post-operative Treatment of Entry-flow

All instances of entry-flow should be evaluated promptly with an angiogram, and if necessary a selective angiogram, to determine the origin of the flow. The completion angiogram should be examined carefully for entry-flow.

Type I entry-flow should be promptly considered for treatment using additional balloon seating or if necessary, placement of additional stent-graft prostheses (use of Zenith main body extensions is recommended). Placement of embolization coils may be needed to occlude sources of Type II entry-flow and collateral flow if the leak is believed to be significant and/or in the presence of an enlarging false lumen. Use of occluder devices (e.g., Amplatzer) to embolize the left subclavian artery has also been reported. Type III entry-flow represents graft or junctional defects and should be promptly considered for treatment with additional ballooning or prostheses. Type IV entry-flow is generally

associated with grafts with a high porosity and is unlikely with the graft component of this system. Secondary/reentry tears may also require coverage with placement of additional stent-graft prostheses in the aorta or covered balloon-expandable and/or self-expanding stents in branch vessels if flow through the tear is significant and/or in the presence of an enlarging false lumen.

6.6 Follow-up Treatment of Entry-flow and Flow Through Secondary Tears

Perfusion of the false lumen should be carefully monitored over the course of the follow-up exams. Treatment for significant entry-flow and flow through secondary tears should be considered especially in the presence of enlarging false lumen (as described in Section 6.5).

6.7 Treatment of Obstruction

Obstruction of the aortic true lumen resulting in end-organ ischemia/malperfusion may require placement of additional stent-graft prostheses or Dissection stents. Obstruction within a branch vessel true lumen resulting in end-organ ischemia/malperfusion may require placement of uncovered balloon-expandable and/or self-expanding stents.

6.8 Secondary Interventions

Some patients may need secondary intervention(s) for treatment of entry-flow, flow through secondary tears, obstruction/compromise of branch vessels, device migration, etc. The use of Zenith stent-graft components is recommended when additional stent-graft placement in the aorta is necessary to extend the length of primary graft coverage or to selectively cover secondary/reentry tears. The placement of uncovered balloon-expandable and/or self-expanding stents may be necessary to assist with true lumen patency in obstructed/malperfused branch vessels. Similarly, the placement of balloon-expandable and/or self-expanding covered stents may be necessary to assist with sealing secondary tears involving branch vessels. The timing and method of such interventions are based on the judgment of the treating physician. If ancillary devices (such as balloons, stents, etc.) are used during these interventions, it is recommended that the Instructions for Use (IFU) of that device be reviewed, and the risks of using that device be considered.

6.9 Follow-up

The study follow-up schedule is provided in Table 3. The suggested guidelines for scheduling the clinical and/or imaging evaluation is as follows: at the time of graft insertion, within 7 days post-procedure, at 30 days (± 10 days), 6 months (180 ± 30 days), 12 months (365 ± 45 days), 2 years (730 ± 60 days), 3 years (1095 ± 60 days), 4 years (1460 ± 90 days), and 5 years (1825 ± 90 days).

Table 3. Study follow-up schedule

	Pre-operative	Intra-operative	Post-procedure	30-day	6-month	12-month	24-month to 5-year ⁵
Clinical Exam	X		X	X	X	X	X
Blood Tests ¹	X		X	X	X	X	X ⁶
Contrast CT Scan	X		X ^{3,4}		X ³	X ³	X ³
Angiography	X ²	X					

1. Including tests to evaluate kidney and liver function.
2. Required only to resolve any uncertainties in anatomical measurements necessary for graft sizing.
3. TEE or non-contrast CT imaging may be used for those patients experiencing documented renal failure (eGFR < 30) or who are otherwise unable to undergo contrast enhanced CT scan.
4. CT must be performed prior to hospital discharge. In case of impaired renal function at the time of discharge, CT may be performed at 30 days.
5. Yearly through 5 years.
6. Required only for patients with malperfusion that has not stabilized.

6.10 Criteria and Procedures for Study Termination

A patient's follow-up in the study will end after:

- 1) Failure to deploy the device + 30 days;
- 2) Conversion to open surgical repair + 30 days;
- 3) Patient withdrawal;
- 4) Patient death;
- 5) Closure of the investigation; or
- 6) Completion of all scheduled clinical and imaging visits through 5 years.

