5.2 Endpoints

The primary safety endpoint will be rate of freedom from major adverse events (see Appendix C, Definitions) at 30 days. The primary effectiveness endpoint will be the survival rate at 30 days. Mortality is the greatest procedural risk associated with alternative treatments and is also the principal outcome any treatment is intended to prevent (up to 50% of patients are at risk for mortality within 48 hours if untreated²).

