5.3 Variables to be Measured to Demonstrate Achievement of Endpoints

To evaluate deployment characteristics, procedural outcome and follow-up, the following data points will be collected:

- 1) Assessment of system performance including: deployment issues, ease of insertion, visualization, and ease of removal;
- 2) Clinical utility measures such as days to discharge from hospital;
- 3) Ancillary equipment needed;
- 4) Adjunctive maneuvers including: balloon dilation of iliac arteries, additional stents required, and additional surgical procedures;
- 5) Complications including major adverse events during procedure and at follow-up;
- 6) Device integrity findings at completion of procedure and follow-up: device patency, stent fracture, and graft kinks;
- 7) Type and sources of entry-flow at procedure and follow-up;
- 8) Dimensions of the true and false lumen over the course of follow-up; and
- 9) Secondary interventions performed.

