5.6 Point of Enrollment

Point of enrollment will be based on the intent-to-treat population, and is defined to include any patient for whom the treatment procedure is initiated. More specifically, once a procedure has begun (i.e., cutdown or percutaneous access initiated), the patient would be included in the intent-to-treat population. The patient's informed consent will be obtained and assessment of the patient's conformance to the inclusion/exclusion criteria will occur prior to the procedure.

Study results will also be analyzed with respect to the consented patient population (i.e., all patients who gave consent to participate in the study, regardless of treatment).

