10.4 Criteria and Procedures for Withdrawal

The investigator must make a reasonable effort to ascertain and record the reason for withdrawal or discontinuation for each patient while fully respecting the subject's rights. The reasons for withdrawal and discontinuation of any patient from the investigation shall be recorded. If such discontinuation is because of problems with safety or lack of effectiveness, that patient shall still be followed-up in the investigation, if possible.

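### Section 6.10 ends follow-up 30 days after failed deployment or open conversion, which conflicts with section 10.4 and leaves late results incomplete for the intent-to-treat population

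*Combined protocol and SAP*

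**What the plan says.** Section 6.10 lists six events that end a patient's follow-up. The first two are "Failure to deploy the device + 30 days" and "Conversion to open surgical repair + 30 days". Patients with neither event, who do not die or withdraw and whose study is not closed, continue to "Completion of all scheduled clinical and imaging visits through 5 years".

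Section 5.6 sets the population at first access: "once a procedure has begun (i.e., cutdown or percutaneous access initiated), the patient would be included in the intent-to-treat population". A failed deployment or a conversion therefore stays in it. The same section also promises an analysis of everyone who consented, whatever treatment they received.

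Section 10.4 deals with withdrawal and discontinuation. Where the reason is a safety problem or lack of effectiveness, it says "that patient shall still be followed-up in the investigation, if possible".

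Late data are clearly meant to be used. Table 3 in section 6.9 schedules visits at 6 and 12 months and then "Yearly through 5 years", and section 5.3 lists "Complications including major adverse events during procedure and at follow-up" among the data to be collected. The secondary objectives in section 3.2 are redacted, so the planned late analyses cannot be seen.

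**The concern.** A patient whose device could not be deployed, or who was converted to open repair, may be alive, consenting and reachable. Section 6.10 nevertheless closes that patient's record 30 days after the event, and in the case of conversion the event may come at any point in the 5 years. The patient is lost by rule, and the rule is triggered by the result of treatment.

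Two things follow. First, after the exit date no survival or MAE summary can cover the whole population that section 5.6 declares. Second, any method that treats the exit as ordinary censoring, or drops these patients, assumes that they share the outlook of patients who stay. Nothing in the plan supports that assumption. If their outlook is worse, late survival and freedom from MAEs will look better than they are in all treated patients. The outcomes may also be hard to recover once contact has stopped.

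**Working it through.** **Step 1. Are the primary tests touched?** Section 5.2 sets the time point: "The primary effectiveness endpoint will be the survival rate at 30 days". The safety endpoint is also read at 30 days. Inputs from section 7.1: one-sided exact binomial test, alpha 0.025, power 0.80; safety goal 51.2%, expected 69.2%; effectiveness goal 79.4%, expected 94.9%. The smallest n meeting both requirements is:

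- Safety: n = 60, success at 39 or more, exact alpha 0.0216, power 0.802.
- Effectiveness: n = 40, success at 37 or more, exact alpha 0.0233, power 0.855.

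Both match the plan's 60 and 40. At n = 67, power is 84.7% for safety (43 or more) and 98.0% for effectiveness (60 or more). None of this uses data after day 30. An exit 30 days after the index procedure, or 30 days after a later conversion, still covers day 30. One detail of scheduling remains: a failed deployment at the index procedure exits at day 30, while the 30-day visit window in section 6.9 runs to day 40.

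**Step 2. What each section does with a failed deployment or conversion.**

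| Section | Effect on this patient |
|---|---|
| 5.6 | In the intent-to-treat population |
| 6.9 | Visits scheduled to 5 years |
| 6.10, items 1 and 2 | Follow-up ends 30 days after the event |
| 10.4 | Follow-up continues if possible, where discontinuation is for safety or lack of effectiveness |

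Failed deployment and conversion are natural examples of the situation in 10.4, though 10.4 does not name them. Nothing says which section prevails.

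**Step 3. Does the missing-data section repair it?** Section 7.4 does not mention exits caused by failure. It prefers case deletion as long as enough patients remain for power on the primary endpoints. With 67 enrolled and 60 needed, that rule would tolerate 67 − 60 = 7 deletions, and it offers no safeguard for late results. Multiple imputation would have no late outcomes from failed or converted patients to learn from beyond their 30 days, so it would borrow from those who stayed. Tipping-point and worst-case analyses are optional.

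**Step 4. How large could the effect be?** The documents give no rate of failure or conversion and no 5-year survival. The following inputs are assumptions: f of 67 patients exit early; 5-year survival is S_stay = 80% in the others and S_exit in those who exit.

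- Reported, with exits censored or deleted: S_stay
- All patients: [(67 − f) × S_stay + f × S_exit] / 67
- Overstatement: (f / 67) × (S_stay − S_exit)

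Example: f = 5, S_exit = 40%. All patients: (62 × 0.80 + 5 × 0.40) / 67 = 51.6 / 67 = 77.0%. Overstatement: 3.0 points.

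| f (share of 67) | S_exit 80% | 60% | 40% |
|---|---|---|---|
| 1 (1.5%) | 0 | 0.3 | 0.6 |
| 3 (4.5%) | 0 | 0.9 | 1.8 |
| 5 (7.5%) | 0 | 1.5 | 3.0 |
| 10 (14.9%) | 0 | 3.0 | 6.0 |

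The table entries are points of overstatement. In the extreme case of no late survivors among those who exit, the range is 1.2 (f = 1) to 11.9 points (f = 10). If all 73 patients form the base, the largest table entry becomes (10 / 73) × 40 = 5.5 points. The formula treats exits as early. A late conversion contributes data until 30 days afterwards, so its effect would generally be smaller.

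**The case against.** The strongest defence is that once the device is absent, ending its follow-up is a legitimate design choice, and the 30-day tail captures the procedural risk of the failure or conversion. Section 10.4 could be read as covering only patients who withdraw or are withdrawn, leaving 6.10 to govern protocol-defined exits. The late analyses are redacted and might, for instance, count conversion as an event. The assumed bias is also modest next to sampling error: at 80% survival and n = 67 the standard error is √(0.80 × 0.20 / 67) = 4.9 points.

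Much of this stands as a limit on the claim. It does not remove the gap. Even on the narrow reading of 10.4, the text does not say which rule applies to these patients. Counting conversion as an event would not supply their later vital status, and a systematic loss of data is not excused by being smaller than the random error.

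Stronger conclusions that a reader might draw are not supported:

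- That late results would describe only device successes. Patients with entry-flow, migration, obstruction or secondary interventions short of conversion stay in follow-up (sections 6.6 to 6.8), and late converters contribute until their exit.
- That the bias must favour the device. It is zero if outlooks are equal and reverses if those who exit do better.
- That section 2.3 shows a poor late outlook after conversion. The mortality it describes is tied to the open procedure, and part or all of it may fall inside the 30-day tail.
- That later outcomes will certainly go unrecorded. Section 10.4, if applied, would keep some of these patients under follow-up.

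**Conclusion.** Sections 6.10 and 10.4 conflict for patients with failed deployment or open conversion. If 6.10 is followed as written, survival and MAE results from 6 months to 5 years are incomplete for the intent-to-treat population, with exit that depends on treatment outcome and no repair in section 7.4. The size of any bias cannot be established from the documents. Under the stated assumptions (1 to 10 exits among 67, 80% survival in those who stay, 40% to 80% in those who exit) late survival is overstated by 0 to 6 points. The hypothesis tests, the performance goals and the sample sizes of 60 and 40 are not affected. The point is a low-cost improvement to the late data and does not challenge the primary conclusions.

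**What to change.** Reconcile section 6.10 with section 10.4:

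1. Reword items 1 and 2 of 6.10 so that failed deployment and conversion end only the device-imaging schedule.
2. Collect vital status and MAEs, with dates, by yearly contact through 5 years for every intent-to-treat patient who has not withdrawn.
3. State that late survival and MAE summaries use this full set, and how failed deployments and conversions enter them.
4. Commit to a worst-case sensitivity analysis for any late status still missing, in place of the optional wording in section 7.4.

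The cost is a yearly telephone or chart contact for what are probably few patients. It needs no added imaging, no extra enrollment and no change to the 30-day tests. The downside is that late rates may look slightly worse.

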7.0 Statistical Considerations

7.1 Sample Size Calculations

The study is designed to enroll 67 patients to evaluate the safety and effectiveness hypotheses (Section 3.3).

For the primary safety endpoint, based on the data from the combined physician-sponsored studies¹, the rate of freedom from 30-day major adverse events (see Appendix

C, Definitions) was estimated to be 61.2%. With a clinically relevant non-inferiority margin of 10%, a performance goal of freedom from 30-day MAE was established to be 51.2%. Sixty patients will be necessary to assess the primary safety hypothesis, under an expected rate of freedom from 30-day MAE at 69.2% (estimated from an on-going clinical trial with the Zenith® Dissection Endovascular System in patients with complicated, type B aortic dissection), with a one-sided exact binomial test, at a type I error rate of 0.025 and a power of 0.8.

For the primary effectiveness endpoint, based on the data from the combined physician-sponsored studies, the survival rate at 30 days was estimated to be 89.4%. With a clinically relevant non-inferiority margin of 10%, a performance goal for 30-day survival was established to be 79.4%. Forty patients will be necessary to assess the primary effectiveness hypothesis, under an expected 30-day survival rate of 94.9% (estimated from an on-going clinical trial with the Zenith® Dissection Endovascular System in patients with complicated, type B aortic dissection), with a one-sided exact binomial test, at a type I error rate of 0.025 and a power of 0.8.

Cook intends to enroll 73 patients, to allow for additional patients who may withdraw or be lost to follow-up, and to account for six previously enrolled patients that would not be eligible for enrollment based on the clarifications provided in Version 4 of the CIP (i.e., patients who were ASA class V or who were without confirmed absence of bowel necrosis at the time of enrollment). While the data from all 73 patients enrolled in the study will be reported, the primary safety and effectiveness hypotheses will be assessed based on the 67 patients enrolled according to the inclusion/exclusion criteria specified in Version 4 of the CIP.

7.2 Performance Goals

The performance goals used in the hypotheses of section 3.3 and the sample size calculations in section 9.1 were derived from the combined physician-sponsored studies. Using those data, the performance goal for the 30-day freedom from major adverse events was 61.2%, while the performance goal for the 30-day survival rate was 89.4%. With a clinically relevant margin of 10%, the performance goals are established as 51.2% and 79.4%, respectively.

7.3 Site-level Poolability

Poolability of data from multiple sites will be verified by examining the primary and secondary safety and effectiveness measures among sites as well as important patient baseline characteristics. Site-level poolability will be considered appropriate provided that these measures are similar among sites.

It is expected that many sites will have too few patients to provide reasonable site-level estimates of primary, secondary, and baseline measures. Each investigative site will be allowed to enroll no more than 14 patients (20% of the total enrollment) to ensure the overall result is not biased by the results from a single site. Pooling of this information will be explored based on hospital size (large versus small), site enrollment (large versus small), type of hospital (community versus teaching), and other group-wise strategies.

It is recognized that patient baseline characteristics may differ among sites, with some sites routinely treating patients with more severe disease progression. It is anticipated that the primary and secondary endpoint measures may be related to covariates that reflect this disease progression, which are in turn related to outcome. Thus, any observed site-specific differences among the primary or secondary endpoints will be checked for confounding with other measured covariates. This can be accomplished using regression models (linear and logistic where appropriate) that include site and other measured covariates as independent variables.

Should one or more sites significantly differ from the rest, then all subsequent analyses will include the discriminating covariate or a covariate to distinguish between the unusual site(s) and those sites that are considered poolable.

7.4 Missing Data

Missing data will be addressed using three primary strategies: 1) estimating missing data with the best available data, 2) case deletion, and 3) multiple imputation.

The first strategy may be used for missing imaging data. Previous clinical trial experience suggests that some portion of the imaging data may not meet the criteria for accurate measurements by the core laboratory. However, it is recognized that the treating physician uses this information to provide the best possible care for the patient.

Therefore, it is reasonable to substitute any missing core laboratory measurements with the corresponding measurements made by the treating physician (or their staff). In addition, the absence or presence of clinical sequelae may provide the required missing

core laboratory assessment of device performance. Furthermore, imaging at subsequent time points may be available, making it possible to infer patient status at the time point of interest. This strategy is a best approximation of the missing data value.

The second strategy is case deletion. If the amount of missing data does not result in a reduction of analyzable patients to a number that is below that required for sufficient statistical power of the primary endpoints, then case deletion will be the method of choice for that analysis.

The third method is multiple imputation. This method will be used to predict missing endpoint or covariate data. It may be that the primary study endpoints may depend upon certain covariates. Therefore, it may be possible to model study endpoints, given a series of related covariates. This model-based imputation exercise may provide estimates of the missing data that can be utilized in estimating event rates and confidence bounds.

Strategies originating from Schafer⁴ will be used, supplemented with notes provided by Schafer.⁵ The computations will be performed using PROC MI and PROC MIANALYZE in SAS version 9.1 or later, or WinBUGS 1.4 or later.

Additional analyses of missing data may be performed as appropriate, including a tipping point analysis and a worst-case analysis.

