5.4 Measures to be Taken to Avoid or Minimize Bias

This study is not randomized or blinded. It is intended to prospectively collect information regarding the safety and effectiveness of the Zenith® Dissection Endovascular System. The study will utilize uniform definitions for study endpoints, event adjudication by an independent clinical events committee, and imaging data analysis by a centralized core laboratory. Study results will be analyzed in accordance with a prospectively defined analysis plan.

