Major Adverse Events: - Myocardial infarction, chronic renal insufficiency/chronic renal failure requiring dialysis, bowel ischemia, stroke, paraplegia or paraparesis, and prolonged (> 72 hours) ventilatory support.

Malperfusion: Malperfusion in the setting of an aortic dissection is defined as one or more of the following¹:

1. Visceral hypoperfusion by an acute abdomen, abdominal pain out of proportion to physical examination findings in setting of radiographic hypoperfusion of mesenteric bed, lactic acidosis attributed to visceral malperfusion, or need for bowel resection.
2. Renal hypoperfusion including oliguria or anuria in setting of rising renal function tests (creatinine or blood urea nitrogen) or radiographic evidence of impaired renal artery blood flow.
3. Lower extremity hypoperfusion indicated by abnormal pulse examinations in conjunction with leg pain, pallor, paresthesias or paralysis.
4. Spinal cord hypoperfusion as noted by altered motor function of one or both of legs attributed to a possible spinal cord source.

MI (Non-Q-Wave): Clinical evidence of a myocardial infarction with elevated peak CK values greater than three times the upper limit of normal with elevated CK-MB (above the institutions upper limit of normal) in the absence of new pathological Q-waves or clinical evidence of a myocardial infarction with troponin greater than three times the upper limit of normal, as determined by the investigator.

MI (Q-Wave): Post-procedure chest pain or other acute symptoms consistent with myocardial ischemia and the presence of new pathological Q-waves in two or more contiguous ECG leads.

Migration (radiographic): Antegrade or retrograde movement of the proximal or distal components of the endoprosthesis > 10 mm relative to anatomical landmarks identified on the first post-operative CT scan as evaluated by core laboratory.

Migration (clinical): Antegrade or retrograde movement of the proximal or distal components of the endoprosthesis resulting in the need for a secondary intervention.

New York Heart Association Classification:

1. Patient with cardiac disease but without resulting limitations of physical activity. Ordinary physical activity does not cause undue fatigue, palpitation, or dyspnea.
2. Patients with cardiac disease resulting in slight limitation of physical activity. They are comfortable at rest; ordinary physical activity results in fatigue, palpitation or dyspnea.

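### Section 7.4 lets absence of symptoms, or a site reading, stand in for a missing core-laboratory result; the symptom rule can understate silent imaging findings

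*Combined protocol and SAP*

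**What the plan says.** Section 7.4 (Missing Data) opens with a strategy limited to imaging: "The first strategy may be used for missing imaging data". The reason given is that "some portion of the imaging data may not meet the criteria for accurate measurements by the core laboratory". Three substitutes are then offered:

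- **Site reading.** It is reasonable to "substitute any missing core laboratory measurements with the corresponding measurements made by the treating physician", or by that physician's staff.
- **Clinical course.** In addition, "the absence or presence of clinical sequelae may provide the required missing" core-laboratory assessment of device performance.
- **Later imaging.** Finally, "imaging at subsequent time points may be available, making it possible to infer patient status at the time point of interest".

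The section sets no order among the three. It requires neither a flag on substituted values nor a core-laboratory-only result. Tipping-point and worst-case analyses are mentioned as optional.

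Section 5.4 acknowledges that the study is neither randomized nor blinded, and lists "imaging data analysis by a centralized core laboratory" among its protections against bias. Appendix C defines radiographic migration as movement of more than 10 mm relative to "anatomical landmarks identified on the first post-operative CT scan as evaluated by core laboratory". It defines clinical migration separately, by the need for a secondary intervention.

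Section 5.3 lists patency, stent fracture, graft kinks, entry-flow and true and false lumen dimensions among the data to be collected. It does not list migration. The secondary objectives (Section 3.2) are redacted.

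**The concern.** An imaging finding and its clinical consequences are different things, and the protocol treats them so. Appendix C has one migration definition based on images and another based on intervention. Its stent-fracture definition is structural and makes no reference to symptoms. Sections 6.5 and 6.6 link treatment of some flow sources to the flow being significant or the false lumen enlarging, so flow without clinical consequence is foreseen. If absence of sequelae may supply the missing assessment, an unread image in a symptom-free patient can be recorded as a negative finding, and silent findings are undercounted.

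The site-reading rule raises a different problem. The trigger is an image that the core laboratory could not measure accurately, and the reading that replaces it comes from the unblinded treating team. Section 5.5 accepts that core-laboratory analysis may contradict the site's pre-operative assessment and that observers will vary on several criteria, so the two readings are not treated as interchangeable. Mixing readers also adds reader differences to measures taken as change over time, such as migration and lumen dimensions.

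What is at stake is how far the imaging-based device-performance results over five years of follow-up can be trusted.

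**Working it through.** **1. Does the rule reach the primary analyses?** The primary endpoints are 30-day survival and 30-day freedom from major adverse events (Section 5.2). The major adverse events in Appendix C are clinical events, and events are adjudicated by a clinical events committee. Neither endpoint is a core-laboratory measurement.

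The plan's own sample sizes (Section 7.1) reproduce. The test is a one-sided exact binomial, and the critical count r is the smallest with P(X ≥ r | performance goal) ≤ 0.025.

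| Endpoint | Goal | Expected | n | r | Exact alpha | Power |
|---|---|---|---|---|---|---|
| Safety | 51.2% | 69.2% | 60 | 39 | 0.0216 | 0.802 |
| Safety | 51.2% | 69.2% | 67 | 43 | 0.0220 | 0.847 |
| Effectiveness | 79.4% | 94.9% | 40 | 37 | 0.0233 | 0.855 |
| Effectiveness | 79.4% | 94.9% | 67 | 60 | 0.0223 | 0.980 |

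None of these inputs is an imaging result, so the figures stand whatever is done with Section 7.4's imaging rule.

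**2. Size of the symptom rule.** The documents give no rate for any imaging finding and no share of missing reads, so every input here is an assumption:

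- p = true rate of the finding, taken as 5–20%
- m = share of core-laboratory reads missing, unrelated to the finding, taken as 5–30%
- Se, Sp = sensitivity and specificity of the substitute against the core laboratory

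Reported rate = p(1 − m) + m[p·Se + (1 − p)(1 − Sp)]

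Shift = −m·p·(1 − Se) + m·(1 − p)(1 − Sp)

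For inference from symptoms with no false positives, Sp = 1 and the shift is −m·p·(1 − Se). Here 1 − Se is the share of findings that are silent. If all are silent (Se = 0), the shift in percentage points, with patients out of 67 in brackets, is:

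| p | m = 5% | m = 10% | m = 20% | m = 30% |
|---|---|---|---|---|
| 5% | −0.25 (0.2) | −0.5 (0.3) | −1.0 (0.7) | −1.5 (1.0) |
| 10% | −0.5 (0.3) | −1.0 (0.7) | −2.0 (1.3) | −3.0 (2.0) |
| 20% | −1.0 (0.7) | −2.0 (1.3) | −4.0 (2.7) | −6.0 (4.0) |

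The largest entry is 0.20 × 0.30 = 0.06, and 0.06 × 67 = 4.02 patients. If half the findings are silent, each entry halves: p = 10% and m = 20% gives a reported 9.0% instead of 8.0%. If none are silent, the shift is zero.

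**3. Direction for site readings.** A physician's reading can produce false positives as well as misses. With p = 10%, m = 20%, Se = 0.8 and Sp = 0.90, the shift is −0.20 × 0.10 × 0.20 + 0.20 × 0.90 × 0.10 = −0.004 + 0.018 = +1.4 points, against the device. With Se = 0.5 and Sp = 0.95 it is −0.010 + 0.009 = −0.1 point. The sign depends on reader accuracy, on which the documents give nothing.

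**4. Consistency of the text.** Under Appendix C, radiographic migration exists only as a core-laboratory evaluation. A site reading is not that. A result inferred from clinical course comes close to the separate clinical-migration definition. The entry-flow and stent-fracture definitions do not name the core laboratory, so the direct conflict is confined to radiographic migration.

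**The case against.** The strongest reply is that Section 7.4 is permissive and narrow. It says what may be done with missing imaging, it allows presence as well as absence of sequelae to count, and it also offers later imaging, which is a sounder basis than symptoms. Many images will exist and have been read at the site even when the core laboratory cannot measure them, so discarding them loses information. The section also prefers case deletion where enough patients remain, and it mentions tipping-point and worst-case analyses. No visible hypothesis, performance goal or sample size uses imaging.

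Most of this stands as a limit on the point, but it does not remove it. Presence of sequelae can add positive findings, yet it does nothing for silent ones. The case-deletion rule is keyed to power for the primary endpoints, so its reach to imaging measures is unclear, and the extra analyses are optional.

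A reader might infer more: that the substitution rule as a whole favours the device, that it contradicts core-laboratory definitions throughout Appendix C, or that Section 5.3 makes migration a listed outcome. The documents support none of these. The direction for physician readings is open (step 3), only one definition names the core laboratory, and Section 5.3 omits migration.

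The reply is also right that restricting results to core-laboratory-evaluable patients is a complete-case analysis. Table 3 in Section 6.9 allows TEE or non-contrast CT in renal failure, while Appendix C defines entry-flow by contrast-enhanced blood, so evaluability may depend on patient condition. The remedy has to allow for that.

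**Conclusion.** The point holds in limited form. If followed, the rule allows absence of symptoms to supply a negative result for a finding that can be silent, and so can understate entry-flow, stent fracture and radiographic migration. It is inconsistent with the radiographic-migration definition and weakens the core-laboratory safeguard in Section 5.4.

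The illustrated undercount runs from nothing to 6 points. The upper end needs a 20% true rate, 30% of reads missing, every finding silent and every missing read scored absent. The range further assumes no false positives and missingness unrelated to the finding. It illustrates scale and does not predict what this trial will show. The effect is confined to imaging-based device-performance measures, and whether any of them is a secondary endpoint cannot be seen. This is a minor but easily corrected weakness.

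**What to change.** In Section 7.4:

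1. Delete the inference of a negative imaging finding from absence of clinical sequelae.
2. Make core-laboratory-evaluable results the main presentation of imaging measures, with the number missing at each visit.
3. Flag site-substituted values and show results that include them as a separate, labelled analysis, so that physician-detected findings on scans the core laboratory could not read are not lost.
4. Make the worst-case or tipping-point analysis mandatory for these measures, because images may not be missing at random.
5. Reconcile the section with Section 5.4 and with the radiographic-migration definition in Appendix C.

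This is a change of analysis wording and needs no new data. The price is smaller denominators for some imaging measures and a main rate that, as a complete-case estimate, may itself be biased. Items 3 and 4 are there to make that visible.
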